12 SOURCE DATA

Source documents are original documents, data, and records from which participants' CRF data are obtained. These include, but are not limited to, hospital records (from which medical history and previous and concurrent medication may be summarized into the CRF), clinical and office charts, laboratory and pharmacy records...etc.

CRF entries will be considered source data if the CRF is the site of the original recording (e.g., there is no other written or electronic record of data).

All documents will be stored safely in confidential conditions. On all study-specific documents, other than the signed consent, the participant will be referred to by the study participant number/code, not by name.

Direct access to source documents will be granted to DATACLin CRO monitoring team as authorized representatives from the sponsor and to regulatory authorities to permit trial-related monitoring, audits and inspections.

13 CLINICAL DATA MANAGEMENT

13.1 DATA MANAGEMENT SYSTEM

Data will be collected and managed using Electronic Data Capture (EDC) technology. The system to be used is “OpenClinica, version 3.14”.

13.2 DATA ENTRY

Data entry and updates will be performed by authorized site staff (the investigator or officially delegated personnel). All personnel to be involved in the data entry will have the proper levels of access, grants and privileges.

Data entry screens development, validation rules programming and maintenance of study database will be the responsibility of DATACLin CRO.

13.3 DATA VALIDATION AND DISCREPANCIES MANAGEMENT BY CRO

The computerized handling of data by DATACLin CRO may generate additional queries automatically through pre-programmed and tested validation rules. Validation rules will be detailed in the Data validation Plan (DVP).

In addition to automatic validation rules, manual/ medical review of data may generate further queries that will be raised on the system as well. Site staff will be responsible for resolving automatic and manual queries by confirming or modifying the data questioned through the EDC system.

13.4 CLINICAL DATA CODING

DATACLin CRO will be responsible for coding of safety data using the latest available version of MedDRA (Medical Dictionary for Regulatory Activities).

Collected trade names of drugs (e.g. concomitant medications) will be also coded to the relevant generic names.

14 QUALITY CONTROL AND QUALITY ASSURANCE

14.1 QUALITY CONTROL

14.1.1 In process quality control of biometrics

As per DataClin CRO SOPs, quality control by an independent qualified reviewer is performed on all biometrics related documents developed internally. This includes study protocol, case report form, informed consent form and study plans. In addition to these documents, database QC is performed automatically (programmed edit checks) and manually (manual review of line listings) to ensure that data is complete and consistent.

14.1.2 Monitoring and site data quality control

Study monitors will perform ongoing source data verification to confirm that critical protocol data entered into the eCRFs by authorized site personnel are accurate, complete, and verifiable from source documents.

100 % Source Data Verification (SDV) will be performed only for Critical Variables.

If specific issues are identified in a certain site, the percentage of Quality Control in the concerned site and/or in all sites must be appropriately increased and corrective actions must be set up.

14.2 QUALITY ASSURANCE

All study procedures will be subject to pre-planned internal audit(s) by DataClin CRO quality assurance team. This covers biometrics phases, clinical operations and overall project management.

15 PHARMACOVIGILANCE

For safety reference; this study will be conducted consistent with The International Conference on Harmonization guideline E2A and 21 CFR Part 312 and WHO Guidelines.

Safety assessments will consist of monitoring and recording adverse events; including serious and non-serious adverse events, measurement of protocol-specified safety laboratory assessments, measurement of protocol-specified vital signs and other protocol-specified measures that are deemed critical to the safety evaluation of the study.

15.1 ADVERSE EVENTS MONITORING

All AEs regardless of seriousness or relationship to Investigational Product (IP), spanning from the signature of the informed consent form, until the end of the study as defined by the protocol for that patient, are to be recorded on the corresponding page(s) included in the CRF and reported as described in the following sections.

For all adverse events, the investigator must pursue and obtain information adequate both to determine the outcome of the adverse event and to assess whether it meets the criteria for classification as a serious adverse event requiring immediate notification to Sponsor or its designated representative.

For all adverse events, sufficient information should be obtained by the investigator to determine the causality of the adverse event. The investigator is required to assess causality. For adverse events with a causal relationship to the Investigational Product, Follow-Up by the investigator is required until the event or its sequelae resolve or stabilize at a level acceptable to the investigator, and Sponsor concurs with that assessment. This may imply that observations will continue beyond the last planned visit per protocol, and that additional investigations may be requested by the Monitoring Team up to as noticed by the sponsor

Whenever possible, diagnosis or single syndrome should be reported instead of symptoms. The Investigator should specify the date of onset, intensity, action taken with respect to IP, corrective treatment/therapy given, additional investigations performed, outcome and his/her opinion as to whether there is a reasonable possibility that the AE was caused by the IP.

15.2 REPORTING PERIOD

For serious adverse events, the reporting period to Sponsor or its designated representative begins from the time that the subject provides informed consent, which is obtained prior to the subject's participation in the study, i.e. prior to undergoing any study-related procedures and/or receiving IP, through and till the end of the Follow-Up Period as specified in the study protocol.

Any serious adverse event occurring any time after the reporting period must be promptly reported if a causal relationship to investigational product is SUSPECTED.

15.3 DEFINITIONS

Adverse Event (AE)

An adverse event is any untoward medical occurrence in a clinical investigation subject administered a product or medical device; the event need not necessarily have a causal relationship with the treatment or usage.

Examples of Adverse Events include but are not limited to:

- Abnormal Lab Test Findings Of Clinical Concerns
- Clinically Significant Symptoms and Signs
- Changes In Physical Examination Findings
- Hypersensitivity
- Progression/Worsening Of Underlying Disease

Additionally, they may include the signs or symptoms resulting from:

- Drug Overdose
- Drug Withdrawal
- Drug Abuse
- Drug Misuse
- Drug Interactions
- Drug Dependency
- Exposure During Pregnancy
- Drug Quality Defect That Has Impact On The Patient Safety

15.4 ADVERSE EVENT OF SPECIAL INTEREST

An Adverse Event of Special Interest (AESI) is an AE (Serious or Non-Serious) of scientific and medical concern specific to the Sponsor's product or program, for which ongoing monitoring and rapid communication by the Investigator to the Sponsor may be appropriate. Such events may require further investigation in order to characterize and understand them. AESIs may be added or removed during a study by Protocol Amendment.

In this study, no Adverse Event of Special Interest will be collected.

15.5 SERIOUS ADVERSE EVENTS

A serious adverse event or serious adverse drug reaction is any untoward medical occurrence at any dose that:

- Results In Death
- Is Life-Threatening (Immediate Risk Of Death)
- Requires Inpatient Hospitalization or Prolongation of Existing Hospitalization
- Results In Persistent Or Significant Disability/Incapacity
- Results In Congenital Anomaly/Birth Defect
- Important Medical Event

Medical and scientific judgment should be exercised in determining whether an event is an important medical event. An important medical event may not be immediately life-threatening and/or result in death or hospitalization. However, if it is determined that the event may jeopardize the subject and/or may require intervention to prevent one of the other adverse event outcomes, the important medical event should be reported as serious.

Examples of such events are intensive treatment in an emergency room or at home for allergic bronchospasm; blood dyscrasias or convulsions that do not result in hospitalization; or development of drug dependency or drug abuse.

15.6 ADVERSE REACTION (ADVERSE DRUG REACTION)

An adverse reaction means any AE caused by a drug. Adverse reactions are a subset of all suspected adverse reactions for which there is reason to conclude that the drug caused the event. This would include all noxious and unintended responses to the Investigational Product related to any dose.

15.7 SUSPECTED ADVERSE REACTION

Suspected adverse reaction means any AE for which there is a reasonable possibility that the drug caused the AE. A suspected adverse reaction implies a judgment by the clinical investigator or study sponsor that there is a reasonable possibility that the AE has a causal relationship with the Investigational Product, though with a lesser degree of certainty about causality, compared to the use of the term “adverse reaction” (or “adverse drug reaction”) as defined above

For the purposes of U.S. IND safety reporting, the meaning of ‘Reasonable Possibility’ is clarified in FDA’s recent changes to CFR 312 by the following examples of types of evidence that would suggest a causal relationship between the drug and the AE, such as:

- A single occurrence of an event that is uncommon and known to be strongly associated with drug exposure (e.g., angioedema)
- One or more occurrences of an event that is not commonly associated with drug exposure, but is otherwise uncommon in the population exposed to the drug (e.g., tendon rupture)
- An aggregate analysis of specific events observed in a clinical trial (such as known consequences of the underlying disease or condition under investigation or other events that commonly occur in the study population independent of drug therapy) that indicates those events occur more frequently in the drug treatment group than in a concurrent or historical control group.

15.8 UNEXPECTED ADVERSE DRUG REACTION

An AE or suspected adverse reaction is considered “Unexpected” if it is not listed in the approved product label (for regulatory-approved, commercially available products) or in the investigator brochure, or is not listed at the specificity or severity that has been observed in a serious adverse event at hand; or, if an investigator brochure is not required or available, is not consistent with the risk information described in the general investigational plan or elsewhere in the available information about the Investigational Product. “Unexpected,” as used in this context, also refers to AEs or suspected adverse reactions that are mentioned in the investigator brochure as occurring with the given class of drugs or may be anticipated from the pharmacological properties of the drug, but are not specifically mentioned as occurring with the particular Investigational Product under investigation.

15.9 ABNORMAL TEST FINDINGS

Treatment-emergent laboratory test abnormalities considered to be of clinical concern should be recorded as AEs in the CRF

The criteria for determining whether an abnormal objective test finding should be reported as an adverse event are as follows:

1. Test result is associated with accompanying symptoms, and/or
2. Test result requires additional diagnostic testing or medical/surgical intervention, and/or
3. Test result leads to a change in study dosing or discontinuation from the study, significant additional concomitant drug treatment, or other therapy, and/or
4. Test result is considered to be an adverse event by the investigator or sponsor.

Merely repeating an abnormal test, in the absence of any of the above conditions, **does not** constitute an adverse event.

Any abnormal test result that is determined to be **an error** does not require reporting as an adverse event.

15.10 HOSPITALIZATION

Adverse events reported from studies associated with hospitalization or prolongations of hospitalization are considered serious. Any initial admission (even if less than 24 hours) to a healthcare facility meets these criteria. Admission also includes transfer within the hospital to an acute/intensive care unit (e.g., from the psychiatric wing to a medical floor, medical floor to a coronary care unit, neurological floor to a tuberculosis unit).

Hospitalization does not include the following:

- Rehabilitation facilities
- Hospice facilities
- Respite care (e.g., caregiver relief)
- Skilled nursing facilities
- Nursing homes
- Routine emergency room admissions
- Same day surgeries (as outpatient/same day/ambulatory procedures).

Hospitalization or prolongation of hospitalization in the absence of a precipitating, clinical adverse event is not in itself a serious adverse event. Examples include:

- Admission for treatment of a preexisting condition not associated with the development of a new adverse event or with a worsening of the preexisting condition (e.g., for work-up of persistent pre-treatment lab abnormality)
- Social admission (e.g., subject has no place to sleep)
- Administrative admission (e.g., for yearly physical exam)
- Protocol-specified admission during a study (e.g., for a procedure required by the study protocol)
- Optional admission not associated with a precipitating clinical adverse event (e.g., for elective cosmetic surgery)
- Pre-planned treatments or surgical procedures should be noted in the baseline documentation for the entire protocol and/or for the individual subject.

Diagnostic and therapeutic non-invasive and invasive procedures, such as surgery, should not be reported as adverse events. However, the medical condition for which the procedure was performed should be reported if it meets the definition of an adverse event. For example, an acute appendicitis that begins during the adverse event reporting period should be reported as the adverse event, and the resulting appendectomy should be recorded as treatment of the adverse event.

15.11 SEVERITY ASSESSMENT

The severity of each AE and laboratory abnormality is to be assessed by the investigator according to following criteria

- Mild (Grade 1): AE or laboratory abnormality that is transient or is easily tolerated on continuation of study drug.
- Moderate (Grade 2): AE or laboratory abnormality that causes the patient discomfort and causes interference with the patient's usual activities.
- Severe (Grade 3): AE or laboratory abnormality that is incapacitating and causes considerable interference with the patient's usual daily activities, and/or may be life-threatening if it worsens.
- Life-Threatening (Grade 4): The AE or laboratory abnormality is life threatening as it exists (i.e., no worsening is required for the abnormality to be life-threatening).
- Death Related AE (Grade 5)

Note the distinction between the severity and the seriousness of an adverse event. A severe event is not necessarily a serious event. For example, a headache may be severe (interferes significantly with subject's usual function) but would not be classified as serious unless it met at least one of the 6 seriousness criteria.

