7.2 SECONDARY

- To explore the optimum dose that is safe in patients with apparent risk factors of NASH giving the most significant effect among two different doses of Heptex.
- To explore the hepatoprotective effect of Heptex as assessed by the change in Fibrosis score.
- To explore the hepatoprotective effect of Heptex as assessed by the occurrence of hepatic complications.

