Reporting of Non-Serious Adverse Event

All Non-Serious Adverse Events will be reported on the adverse event page(s) of the CRF and reported **WITHIN 180 CALENDAR DAYS** to the local regulatory authority.

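### The severity scale sets no numeric limits for laboratory abnormalities: a large symptom-free liver-test rise fits Grade 1 or, by judgement, Grade 3, so grades by arm do not reliably measure hepatotoxicity

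*Protocol*

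**What the plan says.** Section 15.11 of the protocol gives the scale a double scope: "The severity of each AE and laboratory abnormality is to be assessed by the investigator according to following criteria". The two lowest grades rest on tolerability and symptoms:

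- Grade 1: "Mild (Grade 1): AE or laboratory abnormality that is transient or is easily tolerated on continuation of study drug".
- Grade 2: "AE or laboratory abnormality that causes the patient discomfort and causes interference with the patient's usual activities".

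Grade 3 combines incapacity and considerable interference with a prognostic alternative: "and/or may be life-threatening if it worsens". Grade 4 is a present threat to life, and Grade 5 is death. No grade carries a multiple of the upper limit of normal, a multiple of the patient's own starting value, or any other numeric bound.

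Section 7.2 includes the secondary objective "To explore the optimum dose that is safe in patients with apparent risk factors of NASH". Inclusion criterion 4 (Section 9.2) requires raised ALT and/or AST at entry. Under the assessment schedule (Section 2), ALT, AST, bilirubin and INR are measured at screening and at weeks 8, 12, 24 and 36.

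**The concern.** Changes in ALT, AST or bilirubin are often not felt. A scale whose first two steps depend on what the patient tolerates or feels does not order such results by size. The only route upward without symptoms is a judgement about what might follow, and the protocol gives no figure to anchor it.

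The liver is the organ under treatment, and patients enter with raised enzymes. If two investigators can put the same result in different grades, a count of Grade 3 events by arm partly reflects who did the grading. With 47 patients per arm, a few differently graded results could create or remove an apparent difference between the two doses and placebo. That matters for an objective that asks which dose is safe.

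**Working it through.** The protocol states no figure here to reproduce. The check applies each definition in Section 15.11 to one case: a large, symptom-free rise in ALT.

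**Step 1. Each grade in turn.**

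| Grade | Test in Section 15.11 | Large silent rise |
|---|---|---|
| 1 | Transient, or easily tolerated while drug continues | Met |
| 2 | Discomfort and interference with activities | Not met |
| 3, symptom limb | Incapacity and considerable interference | Not met |
| 3, prognostic limb | Could threaten life if it worsens | Met if the investigator judges so |
| 4 | Threatens life as it stands | Met only if judged so |

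The same result can satisfy Grade 1 and Grade 3 together, Grade 2 is closed to it, and no rule chooses between them.

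The first row has a condition. The tolerability limb presupposes that study drug continues; otherwise the rise has to be transient. If drug is stopped and the rise persists, neither limb of Grade 1 applies and Grade 2 remains closed. The result then has a grade only if someone judges that Grade 3 or 4 applies.

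**Step 2. Size of what Grade 1 can hold.** Section 16.3.1 sets the top of the normal ALT range at 43 IU/L. I take this as the upper limit; the two ALT values are illustrative.

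- 50 / 43 = 1.16, about 1.2 times the limit.
- 430 / 43 = 10 times the limit.

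Both fit Grade 1 if symptom-free and either transient or tolerated on continued drug.

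**Step 3. Can the efficacy analyses stand in for the grades?**

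- *Proportion with normal ALT and AST.* Values of 50 and 430 both lie above 43 and count the same.
- *Mean relative change.* A patient going from 50 to 430 has a relative change of (430 − 50) / 50 = 760%. Section 16.1 plans on 43 evaluable patients per arm. If the other 42 fall by x% on average, the arm mean is (760 − 42x) / 43. It is below zero once x exceeds 760 / 42 = 18.1. An average fall above 18.1% in the others therefore leaves the arm showing improvement despite one tenfold value.
- *Mann-Whitney alternative.* That patient counts only as the highest rank, however large the rise.

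These analyses summarise benefit. They do not count large individual rises by arm.

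**The case against.** The strongest reply is that the scale is not purely symptom-based and that liver signals can be seen elsewhere. Much of this stands.

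- A reader might infer that laboratory results are graded only by how the patient feels. That is true of Grades 1 and 2 only. Grade 3 has a prognostic limb and Grade 4 rests on threat to life, so a silent rise can be graded high. The defect is overlap without a rule.
- A reader might infer that the trial cannot show hepatotoxicity by dose. The document does not support that. ALT and AST change, ALT and AST normalisation and hepatic complications are all compared by arm (Section 16.3), and listings of individual data are planned (Section 16.4). The protocol describes no severity tables; these may be in an analysis plan that is not shown.
- A reader might infer from "In this study, no Adverse Event of Special Interest will be collected", and from the 180-day limit in Section 15.17 for non-serious events, that a silent liver signal has no quick route. It does have one. Section 15.9 makes a result an adverse event if it needs further testing, changes dosing, or is considered one by the investigator or sponsor, with no symptoms required. Section 15.5 allows it to be serious as an important medical event, which brings the 24-hour notification in Section 15.17. The 180 days is a limit for reporting to the authority and does not measure delay in detection. Having no events of special interest is an openly stated pharmacovigilance choice.

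It can also be said that an analysis plan could tabulate laboratory values by size. It could, but the grades that investigators record under Section 15.11 would be unchanged, and two sets of severity information would then disagree. Listings show individual values but do not compare arms.

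**Conclusion.** The point holds in a limited form. Section 15.11 states a rule for grading laboratory abnormalities, and that rule gives inconsistent answers. One large asymptomatic rise fits Grade 1, cannot be Grade 2, and may be Grade 3 by judgement. The possible disagreement spans two grades, and Grade 1 alone can hold ALT values from 1.2 to 10 times the protocol's cut-off. Recorded severity by arm is therefore not a reliable measure of hepatotoxicity for the safe-dose objective, and the arm means do not fill the gap.

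This rests on three assumptions: that the rise causes no symptoms, that it is transient or tolerated on continued drug, and that 43 IU/L serves as the upper limit. The protocol does not allow an estimate of how often such rises will occur or how far investigators will differ, so no effect on a comparison between arms is claimed.

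**What to change.** In Section 15.11:

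1. Restrict the symptom-based scale to clinical adverse events.
2. Grade laboratory abnormalities by value on a published numeric toxicity scale that the protocol names, derived by program from results already in the electronic data capture system.
3. Show ALT, AST and bilirubin as multiples of both the upper limit and the patient's own pre-treatment value. Entry requires raised ALT and/or AST, so a multiple of the upper limit alone would grade some patients before they take any drug. The schedule has no liver tests at week 0, so the pre-treatment value is the screening result, and the text should say so.

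This changes how results are graded, not how patients are managed. It needs no new samples or visits. The cost is a protocol wording change, a small amount of programming and a second grading scale to explain to sites and readers.
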